6. TREATMENTS

6.1 Investigational Medicinal Product (IMP) Details

Neoadjuvant finasteride and bicalutamide are used within standard practice. However, they are considered investigational medicinal products within CHRONOS as they are being used to discover, verify and compare their clinical effects with focal therapy.

CHRONOS-B (only)

- Arm 2 (Intervention arm): **Neoadjuvant finasteride** 5mg once daily for a minimum of 12 weeks (84 days) followed by focal therapy.
- Arm 3 (Intervention arm): **Neoadjuvant bicalutamide** 50mg once daily therapy for a minimum of 12 weeks (84 days) followed by focal therapy.

6.2 Labelling and Packaging

Neoadjuvant finasteride and bicalutamide are open label and will be dispensed from the site local pharmacy stock according to normal pharmacy protocol. Any brand/ formulary of finasteride and bicalutamide are permissible within CHRONOS B.

6.3 Storage and Dispensing

Short Title: IP4 - CHRONOS	Protocol No: 19CX5006	Sponsor: Imperial College London	Version: 5.0 Date: 13 th July 2022
			10 daily 2022

Neoadjuvant finasteride and bicalutamide will be stored and dispensed according to normal pharmacy protocols. Patients should store their medication as indicated in the Summary of Product Characteristics (SmPC) leaflet which is included in the standard packaging.

6.4 Dosage, Duration and Compliance

Patients randomised to CHRONOS-B Arm 2

- Neoadjuvant finasteride 5mg once daily for 12 weeks (84 days) therapy followed by focal therapy. The medication will be prescribed and dispensed within 24 hours of randomisation.

Patients randomised to CHRONOS-B Arm 3

- Neoadjuvant bicalutamide 50mg once daily for 12 weeks (84 days) followed by focal therapy. The medication will be prescribed and dispensed within 24 hours of randomisation.

As part of compliance assessment, patients will be asked to return their blister packs after the 12 week treatment duration is complete. Ideally, they should provide them to the local research team at the subsequent focal therapy visit. Compliance will also be reported regularly in the CRF.

6.5 Accountability

The returned blister packs should be kept in a safe location at the local site, with the Patient Identifier number clearly marked on the packaging and the paper and electronic CRF accountability logs completed. Returned blister packs must be accessible to the Study Monitor for accountability assessment during monitoring visits.

6.6 Drug Interactions/ Precautions/ Contraindications

Finasteride

Interactions:

No drug interactions of clinical importance have been identified.

Precautions:

Obstructive uropathy

Advised for patients to use effective contraception during treatment due to risk of morphological changes in spermatozoa

Contraindications:

Hypersensitivity reaction to 5-alpha reductase inhibitors

Bicalutamide

Interactions:

Severe: none identified Moderate: Lomitapide* Mild: none identified

*theoretical

Precautions:

Risk of photosensitivity- advised to avoid exposure to UV light and sunlight Monitoring of liver function tests required- accumulation may occur in moderate to severe hepatic impairment

Protocol No: 19CX5006 v5.0 13th July 2022

Short Title: IP4 - CHRONOS	Protocol No: 19CX5006	Sponsor: Imperial College London	Version: 5.0 Date: 13 th July 2022
			13 July 2022

Advised for patients to use effective contraception during treatment due to risk of morphological changes in spermatozoa

No dose adjustment is required in the elderly patients or patients with renal impairment

Contraindications:

Hypersensitivity to anti-androgen therapy

6.7 Overdose of IMP

Finasteride

There is no known antidote and therefore symptomatic and supportive treatment should be given.

Bicalutamide

There is no known antidote and therefore symptomatic and supportive treatment should be given.

6.8 Dose Modification for Toxicity

Finasteride

No dose changes are recommended for renal or hepatic impairment

Bicalutamide

No dose changes are recommended for renal impairment Advised caution in patients with moderate- severe hepatic impairment

6.9 IMP Drug Administration

Patients will self-administer neoadjuvant finasteride and bicalutamide by mouth. The local research physician/nurse will explain the treatment frequency and duration to the patient.

6.10 Non-Investigational Medicinal Product (Non-IMP) Details

Standard of care treatments will be prescribed as per their approved use. The study will not mandate type or dosage of any standard of care medication or treatment for treatment of prostate cancer. Physicians will be asked to declare which they will use upfront prior to randomisation and for this to be documented in the trial CRF.

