To date, approximately 90% of FT cases in the UK are intermediate or low-volume high-risk cancers. There is currently no evidence comparing FT to standard of care active treatments such as radiotherapy or prostatectomy in men with clinically significant cancer. A recently completed pilot RCT comparing FT to prostatectomy (called PART) had a feasibility objective to meet a recruitment rate of 50% of men approached. However, after screening 356, 244 were eligible, of whom only 70 men accepted randomisation. 20% of those randomised to prostatectomy refused their allocation, but none declined in the FT arm. We previously reviewed 12 RCTs in which very different interventions in localised prostate cancer were compared, but failed to accrue. We proposed that there was a need to ensure novel trial designs that embrace clinical and patient equipoise [16].

In addition to the need for RCTs comparing FT against standard care with radical radiotherapy/prostatectomy, there clearly needs to be a deeper understanding as to why failure occurs after FT and to develop strategies to reduce the need for further treatment. Failure can occur due to, a) heat-sink effects countering thermal effects, b) swelling during treatment causing skip-lesions or, c) progressive/de-novo out-of-field development of significant cancers. Strategies that decrease neovasculature, reduce tumour volume, or potentiate the immune response induced by ablation might complement FT to reduce failure [16-28]).

If FT fails it can be redone to the same area; an attribute that is missing from radical therapies. If redo FT fails, then men can still proceed to radical therapy. Over a 5-year median follow-up, redo FT rates are approximately 20-30% and salvage radical or systemic therapy occurs in 10%. Metastases are uncommon (3%) and cancer-specific survival 100% over the same period of time [10]. By comparison, the reported failure rate requiring further treatment after radical therapy is about 10-20% over a 5-10 years median follow-up. Currently 4-5% of cases have out-of-field failure at a median of 5 years [29], which might represent progression or may represent the false-negative rates of mpMRI and biopsy used to localise disease prior to focal therapy. Although many patients accept these rates of further treatments after FT, there is a need to investigate strategies that might optimise FT further to reduce patient and healthcare burden.

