2.5 Main Study Primary Endpoints

CHRONOS-A

Progression-Free Survival (PFS) with progression defined as biochemical failure (radical therapies only), salvage therapy (local or systemic) or prostate cancer metastases or prostate cancer specific mortality. Salvage local therapy following focal therapy will be defined as surgery or radiotherapy or 3 or more focal therapy sessions. Any radiotherapy given after prostatectomy will be counted as an event.

CHRONOS-B

Failure-Free survival (FFS) with failure defined as time to one further focal therapy session or salvage therapy (local radiotherapy or surgery, or systemic) or prostate cancer metastases or prostate cancer specific mortality.

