5.8 Treatment

CHRONOS-A

- Arm 1 (Control arm): Radical therapy (prostatectomy or radiotherapy [external beam or brachytherapy]). The type of radical therapy will be determined by physician or patient preference.
 - In radiotherapy patients, neoadjuvant ADT permitted and if given, minimum 3 months and maximum 6 months duration.
 - We anticipate lymph node treatment in this group is not required but 'for cause lymph node treatment will be permissible if strong clinical preference is demonstrated.
 - If an extended lymph node dissection is anticipated this will need to be discussed in a central review by the surgery subgroup.
 - As per Radiotherapy Trials Quality Assurance (RTTQA) centres and physicians delivering radiotherapy will need to be approved.
 - o Radiotherapy detailed protocols will be set out in a separate SOP.
 - Surgeons and surgical centres currently are approved as a national commissioning programme so any centre or surgeon permitted to carry out radical prostatectomy in standard NHS practice will be permitted to deliver prostatectomy within this trial.
 - o Prostatectomy details will be set out in a separate SOP.
- Arm 2 (Intervention arm): Focal therapy alone (high intensity focused ultrasound [HIFU] or cryotherapy or other validated energy modality as per physician/patient decision/choice. Other energy modality will only be added after TSC and TMG approval and a substantial amendment approved by all required bodies.
 - A second treatment either in-field or out-of-field will be permitted either after the MRI and optional biopsy showing clinically significant cancer at 12-months or due to suspicion of residual or new contralateral disease at a future date with a positive biopsy for clinically significant cancer.
 - Cryotherapy can be used after HIFU and HIFU can be used after cryotherapy.
 This second focal therapy session will be part of the focal therapy intervention
 - Where patients have undergone hemiablation to one lobe and then undergo hemiablation of the contralateral lobe will be designated as failure of focal therapy
 - Focal therapy details will be set out in a separate SOP.

Patients previously or currently on 5 alpha reductase inhibitors or anti-androgens, or LHRH agonists or LHRH antagonists are still eligible for CHRONOS A.

CHRONOS-B

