IP4 - CHRONOS 19CX5006 Imperial College London Date: 13 th July 2022	Short Title: IP4 - CHRONOS	Protocol No: 19CX5006	Sponsor: Imperial College London	
---	-------------------------------	--------------------------	-------------------------------------	--

Biochemical Failure

For the purposes of this trial, biochemical failure will be defined after surgery and radiotherapy/ brachytherapy as per standard care. Early adjuvant or salvage therapy can be given prior to biochemical failure if clinically determined through an MDT. These will count as events for purposes of PFS. Focal therapy does not have a validated definition for biochemical failure.

- Radiotherapy/ brachytherapy: PSA nadir plus 2ng/ml as per Phoenix definition
- Surgery PSA >/=0.2ng/ml at any time-point after surgery

Confirming biochemical failure

The timing and thus assessment of PSA needs to be considered because rises in PSA can occur due to non-cancer related causes such as after procedures, biopsies or urinary tract infection (UTIs). Confirmatory samples are needed in all cases of a rising PSA prior to assigning an outcome of biochemical failure. After biochemical failure is confirmed for the first time it need not be reported again.

In the case that the raised PSA value reaches the biochemical failure value, a second confirmatory PSA test should be performed after at least 1 week or after 4 weeks after the completion of treatment in cases of UTIs, procedures or biopsies. Biochemical failure is confirmed if the second value also confirms this. The date of biochemical failure should be provided as the date of the **first PSA** that fulfilled the definition for failure.

If salvage treatment does start before the trial definition of biochemical failure is met then report the closest PSA value prior to the treatment start date as the progression value.

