Planned interim analyses for education: there will be a review of recruitment into each research arm and these results as well as the qualitative outcomes will be used for submission for a research doctoral thesis of [name] supervised by the Chief Investigator of this trial. The thesis will be embargoed to public release as deemed necessary by the TSC/DMC.

CHRONOS-B: Interim monitoring and analyses: For each research comparison one formal intermediate analysis is planned, where an activity "hurdle" is determined on the intermediate primary outcome measure, FFS. Each research arm needs to pass this in order to continue recruitment. This will initially be timed according to the observed number of interim events required for a formal interim analysis (Table 2).

Table 2: Guidelines for stopping accrual and trigger for analysis

Stage	Arm Ratio	Target HR	One-sided alpha	Power	HR cut-point	Control arm events
2 Activity	1:1	0.67	0.45	95%	>0.974	~47FFS
3 Efficacy	1:1	0.67	0.025	85%	-	~120FFS
Overall	-	-	0.044	83%	-	-

For each comparison that continues recruitment into its final efficacy stage, the final analysis will be triggered by a pre-specified number of definitive primary outcome events being reported for the relevant patients on the control arm of that comparison (Table 2).

Further details of the planned analysis of the secondary outcomes and methods for dealing with missing data will be given in the Statistical Analysis Plan. Any deviation from the statistical analysis plan will be described and the reason for the deviation explained.

i. Primary Outcome Measure Analysis

The primary endpoint (PFS or FFS) analysis consists of a Cox proportional hazard model to investigate the effect of the intervention on PFS/FFS adjusted by the stratification variables.

The assumption of proportional-hazards (PH) will be tested and appropriate methods applied to the data in the case of any violation. If there is no evidence of non-PH in the treatment effect, the HR for the adjusted Cox model takes primacy. If there is evidence of non-proportional hazards in the treatment effect, the HRs are difficult to interpret and the

Short Title:	Protocol No:	Sponsor:	Version: 5.0
IP4 - CHRONOS	19CX5006	Imperial College London	Date:
			13 th July 2022

restricted mean survival time (RMST) constructed from a flexible parametric model with time varying treatment effects will take primacy.

ii. Secondary Outcome Measure Analysis

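### CHRONOS-A: the standard treatment declared before randomisation has no planned use, so focal therapy cannot be compared with surgery or with radiotherapy on a randomised basis

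*Protocol*

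**What the plan says.** **Comparator.** Protocol section 5.8 defines the CHRONOS-A control as radical therapy and adds: "The type of radical therapy will be determined by physician or patient preference". No mix of modalities is fixed.

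**Declaration.** Section 6.10 leaves the type of standard-of-care treatment open, then says: "Physicians will be asked to declare which they will use upfront prior to randomisation and for this to be documented in the trial CRF".

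**Event rules.** These differ by modality. Section 5.9 has "Radiotherapy/ brachytherapy: PSA nadir plus 2ng/ml as per Phoenix definition" and "Surgery PSA >/=0.2ng/ml at any time-point after surgery". Section 2.5 adds for surgery: "Any radiotherapy given after prostatectomy will be counted as an event". For the other arm, section 5.9 says: "Focal therapy does not have a validated definition for biochemical failure".

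**Randomisation and analysis.** Section 5.3 stratifies by grade, local stage and, in CHRONOS-A, 5-alpha reductase inhibitor use. Under section 8.3 the primary Cox model is fitted "to investigate the effect of the intervention on PFS/FFS adjusted by the stratification variables". The paragraph there on interim and subgroup analyses names no subgroup.

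**Pilot SAP.** The baseline variables (SAP 8.1) do not include a declared modality. SAP 8.3 lists the radical treatment delivered, taken from a radiotherapy/brachytherapy log and a prostatectomy log. Tables 2.4 and 2.8 have Focal, Radical and Total columns only.

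**The concern.** A man choosing radical treatment chooses surgery or radiotherapy, not a mixture. A pooled non-inferiority result is an average over whatever mix the sites happen to use, with control events counted under two sets of rules. Readers will ask whether it holds against each modality.

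A modality recorded before randomisation, for men in both arms, would let that be examined without losing the protection of randomisation. The protocol appears to plan such a record but gives it no use. Timing matters because pilot men carry forward into the main stage (section 8.1.1). If the field is missing or ambiguous for them, it cannot be filled in later free of knowledge of allocation.

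**Working it through.** **1. Where the declared value appears**

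| Place | Declared modality used? |
|---|---|
| Protocol 6.10 | Declared and documented (modality not named) |
| Protocol 5.3, SAP 6.8 (stratification) | No |
| Protocol 8.3 (primary model, adjusted analysis) | No; stratification variables only |
| Protocol 8.3 (subgroups) | None named |
| SAP 8.1, 8.3, Tables 1.1, 2.4, 2.8 | No |

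**2. Why treatment received cannot replace it.** Radical modality received exists only in the control arm, so there is no matching group of focal-arm men. Comparing all focal men with, say, the men who had surgery sets a whole randomised arm against a part of the other arm selected by preference. Grouping both arms by a value fixed before allocation avoids this.

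**3. How far the mix could matter (assumptions only).** The documents give no surgery share, and section 8.1.2 says PFS is similar after the two treatments. If both are 85%, the mix has no effect on the margin.
- Assume 90% after radiotherapy, 80% after surgery, half each. Pooled = 0.5×90 + 0.5×80 = 85%. A focal PFS of 82% is 3 points below the pooled rate (inside the 5-point margin) and 8 below radiotherapy.
- Assume the 85% that section 8.1.2 adopts for radiotherapy and the 75% for surgery that it quotes from another pilot trial's design. With a 30% to 70% surgery share, pooled PFS is 82% to 78%. The lowest focal PFS within the margin is 77% to 73%, which is 8 to 12 points below radiotherapy.

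**4. Precision of by-modality estimates.** The plan's own figure is 136 events (section 8.1.2). It does not follow from the stated 85% and 5 points. The hazard ratio margin is ln(0.80)/ln(0.85) = 1.373, and Schoenfeld's formula with one-sided 0.05 and 80% power gives 4×(1.645+0.842)²/(ln 1.373)² ≈ 247. Freedman's formula with 90% against 85% (hazard ratio 1.5425) does give 136. That is a separate matter; 136 is used here as stated.

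With d events in a declared group and 1:1 arms, SE(ln HR) ≈ 2/√d, so the 95% factor is exp(1.96×2/√d).
- Even split (assumed), d = 68: exp(3.92/8.246) = 1.61.
- 30:70 split (assumed), d = 41 and 95: factors 1.84 and 1.50.
- Ratio of the two hazard ratios, even split: exp(1.96×√(4/68 + 4/68)) = 1.96.
- Power for non-inferiority within one group at d = 68 (Freedman, one-sided 0.05): 36% at hazard ratio margin 1.373 and 55% at 1.5425.

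**5. Pilot compliance.** SAP 9.3 judges compliance on the lower confidence limit, by arm and by trial: 80% or more is viable, 70% to 80% calls for remedial work. Suppose 15 of 30 radical men are declared for surgery and 3 of those refuse, with no other refusals. The surgery group is 12/15 (80%) and the arm is 27/30 (90%). The arm's lower 95% limit is 79.3% (Wald), 74.4% (Wilson) or 73.5% (exact), so all three fall in the remedial band. For a group of 15, even 15/15 has a lower limit of 79.6% (Wilson, 15/(15+3.84)) or 78.2% (exact, 0.025^(1/15)).

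**6. What counts as a PFS event.** Sections 2.5 and 5.9 count biochemical failure after radical therapy. Sections 2.2 and 8.1.2 define PFS by salvage therapy, metastases or prostate cancer death, without it.

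**The case against.** The strongest reply is that the trial asks about focal therapy against radical therapy as a strategy. The aims, objectives and treatment sections all say so, and the randomised comparison for that question is sound. This stands. A reader might infer that pooling invalidates CHRONOS-A or its non-inferiority test; the documents do not support that.

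A reader might also infer that the pilot compliance gate would hide refusal concentrated in surgery. The cited earlier pilot did find that "20% of those randomised to prostatectomy refused their allocation". But prostatectomy was its only comparator, whereas here the radical modality follows preference, so carrying the rate across is an assumption. Even on that assumption, 27/30 already triggers remedial work at arm level. What the pooled table lacks is an indication of where to direct that work; the treatment logs and reasons for withdrawal may supply part of it.

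Three further points have force:
- Section 6.10 refers to standard-of-care treatment in general. It does not name surgery or radiotherapy, or say that the declaration is made for each patient, so reading it as intended modality is an inference.
- The only SAP available covers the pilot. Non-use is therefore firm for stratification and the primary model, but provisional for main-stage subgroups.
- If the section 8.1.2 definition of PFS governs, the different PSA thresholds largely drop out, although the modalities stay pooled. A covariate would not harmonise event ascertainment in any case.

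Imprecision is also a fair objection. At a true hazard ratio of 1.0 and an even split, the upper limit would be about 1.61, above the 1.37 implied by 85% and 80%. The by-modality results can support the primary result but cannot establish non-inferiority within a modality.

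**Conclusion.** The point holds as a missed use of planned baseline information. The primary comparison is valid. However, a value apparently declared before randomisation has no role in stratification, the primary model or the pilot SAP. Any look at surgery or radiotherapy separately would therefore fall back on treatment received, without randomisation.

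Using the declared value would give unconfounded but imprecise estimates: about ×/÷1.6 with an even split of the stated 136 events, or ×/÷1.5 and ×/÷1.8 with a 70:30 split. The interaction test would have low power. This rests on the declaration being the intended modality and being captured in both arms, on the stated event count, and on an assumed split. The 90%/80% and 85%/75% examples show only what could happen; the protocol's planning assumption is that the two modalities are similar.

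**What to change.** 1. In Protocol 6.10, state that the declaration is the intended radical modality (prostatectomy or radiotherapy/brachytherapy), recorded for every CHRONOS-A man before randomisation. Confirm that the CRF field exists in that form for men already randomised.
2. In Protocol 8.3, add declared modality as a covariate in the CHRONOS-A Cox model. Pre-specify the focal-versus-radical estimate within each declared group, in all randomised men, with an interaction test, labelled supportive. Carry this into the main-stage SAP.
3. Show SAP Tables 2.4 and 2.8 by declared modality, descriptively, without applying the 80% gate to these subgroups.
4. Reconcile Protocol sections 2.2, 2.5, 5.9 and 8.1.2 on whether biochemical failure is a PFS event.

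The cost is amendment wording, one clarified CRF field and some extra table columns, with no added patients or procedures. If the field turns out not to be held for each patient, it must be added. The drawback is that the by-modality results will be imprecise and open to over-reading, so the supportive label has to be kept in reporting.

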6.11 Permanent Discontinuation of Study Treatment and Withdrawal from Study

i. Permanent discontinuation of study treatment

Subjects may discontinue study treatment for the following reasons:

- At the request of the subject.
- Allergic reaction to IMP
- If the investigator considers that a subject's health will be compromised due to adverse events or concomitant illness that develops after entering the study.

ii. Withdrawal from Study

Withdrawal from the study refers to discontinuation of study treatment and study procedures and can occur for the following reasons:

- Subject decision
- Loss to follow-up

Short Title: IP4 - CHRONOS	Protocol No: 19CX5006	Sponsor: Imperial College London	Version: 5.0 Date: 13 th July 2022
			10 Gary 2022

iii. Procedures for Withdrawal from Study

Every effort should be made to follow-up all patients who have been randomised. Patients should, if possible, remain under the care of an oncologist or urologist for the duration of the trial. If care of a patient is returned to the GP, it is the responsibility of the responsible clinician who obtained the patient's consent to participate in the trial to ensure that all relevant data collection forms are completed. Nurse-led follow-up is permitted and should be conducted in line with local practice and procedures.

If the patient moves away from the local area, arrangements should be made for trial followup to be undertaken by their new local centre. Details of other participating centres can be obtained from the Study Manager. If the responsible clinician moves, appropriate arrangements should be made to arrange for trial follow-up to continue at the centre.

All efforts should be made to preserve the patient's initial consent for long-term survival information to be flagged through national registries, for example NHS Digital (previously the Health and Social Care Information Centre); Office of National Statistics (ONS) in England/Wales; General Register Office in Scotland; Hospital Episode Statistics (HES) or Public Health England.

In order to do this we will provide all patients an optional consent to provide identifiable information for us to trace the patient on the National Health Service Care Register (NHSCR) for an additional 10 years.

We will also ask patients whether or not they give permission to be contacted by a member of the study research team within 10 years of signing their consent form, after the study has ended to assess their willingness to complete a questionnaire on their health status and quality of life. This will allow us to track what happens after the study finishes to observe if anyone gets cancer in future and about the type of cancer and the treatment they have had. Results of the optional health status check will also help us to refer to any future upcoming studies.

